9. POTENTIAL RISKS TO PATIENTS

We anticipate minimal risk for patients. In fact, our study seeks to improve safety for patients through the use of a home monitoring device with integration to the electronic health record. Participation in this study is voluntary and refusal to participate will not result in penalties or loss of care.

Although measures will be in place to minimize risk, it is possible that health information could be improperly disclosed. We will gather only essential information necessary to complete the study.

10. BENEFITS/OUTCOMES

Potential benefits may include:

- Patients may have better knowledge and control of their BP
- Pharmacists may feel good about helping patients improve their BP
- Patients may have a more trusting relationship with their pharmacist
- The Family Medicine Department might improve BP outcomes and quality of care
- There may be less morbidity and mortality from out-of-control BP
- Patients may be satisfied with home telemedicine

11. DATA MANAGEMENT AND ANALYSIS

- Primary Objective: Preliminary data to design a larger, funded study
 - Captured data and information will be collected in such a way as to make it useful for putting forth a cogent argument for a larger effort.
- BP readings will be captured automatically in Epic
- Mean BP readings will be calculated and compared for the pre- and post-periods, as will the number of patients in and out of blood pressure control
- Pre- and post-study data will be analyzed using a comparison of means (2-tail t-test) and chi-square for comparing low compliant patients (for using the devices) with high compliant patients. The post-study patient satisfaction data will be analyzed using descriptive statistics.

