3. STUDY OBJECTIVES

Primary Objective

- To produce preliminary data to design a larger, funded study

Secondary Objectives

- To assess patient comfort in using home telemonitoring for blood pressure combined with pharmacist counseling and monitoring using a survey instrument with a Likert scale
- To assess the ability to collect and monitor hypertension data using Bluetooth enabled mobile health technology
- To determine if blood pressure readings improve with pharmacist interventions

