4. STUDY DESIGN

This is a pragmatic before and after trial with the patient serving as their own control

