5. STUDY POPULATION

We are aiming to enroll 20 patient participants for this pilot study. To be eligible for participation, enrollees must be ≥ 18 years old, have a smartphone compatible with the mobile intervention, have been previously diagnosed with hypertension, have uncontrolled hypertension (SBP > 130 mmHg and/or DBP > 80 mmHg), be under the care of a primary care physician in the Family Medicine

Department of the USF Morsani Center for Advanced Care, have had at least one prescription filled at Pharmacy Plus within the last six months, and speak English fluently.

Patients will be excluded if they are already under the care of a clinical pharmacist in the Family Medicine department, are pregnant, or have a serious existing medical condition(s) that may affect their ability to self-monitor their blood pressure (for example, stroke, dementia).

Recruitment

A list of potential patients (Family Medicine patients with diagnosis of hypertension who have had at least one prescription filled at Pharmacy Plus within the last 6 months) will be generated by the Epic support team and identified through the electronic medical records system as well as the pharmacy prescription database. The pharmacists from Pharmacy Plus on this study or 4th year pharmacy students on their Ambulatory Care or Community Pharmacy Rotation will call patients on this list and will discover if the patient meets the final qualification for the study (has a smart phone or other smart device) and is interested in being a part of the study. This is not cold calling, as this list includes eligible patients who have had a prescription filled at Pharmacy Plus within the last 6 months. Each patient on this list has interacted with the pharmacists at Pharmacy Plus when the medication was dispensed. The pharmacists have an established relationship with these patients, as they are involved with the care of these patients. They are involved with the treatment of these patients as they provide pharmacy services when dispensing medications and counseling the patients, as well as some medical services such as vaccine administration.. [name], who practices in the Family Medicine department, is the physician on this study and is aware that these patients will be contacted via phone. We will not be obtaining verbal consent to participate during this phone call.

Enrollment

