6. INTERVENTIONS

Devices

- Smart Phones with Apple Health Software will be used to monitor blood pressure once a day, and results will be sent automatically to the patients EHR (Epic)
- The Omron 10 Series Wireless Upper Arm Blood Pressure Device will be given to the patient to monitor blood pressure at home daily

Pre- and Post-surveys

- A pre- and post-survey will be given at the initial and final in-person appointments, respectively
- These surveys will collect basic patient demographics, knowledge of blood pressure, comfort with checking blood pressure at home, and previous experience working with a pharmacist

Pharmacist Management

- Review of evidence-based therapy and recommendations for improvement if needed
- Educate the patients on how to monitor their blood pressure with their Bluetooth enabled home blood pressure monitor and smart phones

- Patients will be scheduled for a one-hour in-person appointment for the initial study visit where informed consent will be obtained, and for the final study visit
 - At the final study visit, the patients will complete a post-study survey and be given a \$25 gift card upon return of the blood pressure device
- Review results once per week
 - If any patient has an SBP reading > 160 mmHg or DBP > 100 mmHg, they will be instructed to wait five minutes and then recheck their BP. If the BP readings exceed these thresholds for three days in a row, the patients should contact their primary care provider in the clinic for further management.
 - If SBP > 180 mmHg and/or DBP > 120 mmHg, patients will be instructed to call 911 or have someone drive them to the ER immediately
 - There will not be alerts sent to the study pharmacists if the blood pressure readings are above these thresholds
- Follow-up with patients once per week for six (6) weeks via scheduled 20-minute telehealth appointment with each patient via the HIPAA secure and compliant platform, VSee
 - During this telehealth appointment, the study pharmacists will counsel the patients on their blood pressure readings for that week and provide lifestyle education focusing on patient-specific diet and exercise recommendations
- The total duration of the study will be eight (8) weeks

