7. EXPECTED RESULTS

The Hypotheses – It is expected that:

- The study will be able to produce data in order to design a larger, funded study
- Patients will express comfort in using home telemonitoring
- The pharmacists will be able to collect and monitor hypertension data using mobile health technology
- A statistically significant ($p < 0.05$) greater proportion of patients in the after study period will be in proper control of their hypertension ($< 130/80$ mmHg) than in the before study period

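### The before period is not defined; if it is the reading that qualified the patient, control starts at 0 of 20 by eligibility and p < 0.05 can arise from retesting alone

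*Combined protocol and SAP*

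**What the plan says.** Section 4 describes a "before and after trial with the patient serving as their own control". To enter, a patient must "have uncontrolled hypertension (SBP > 130 mmHg and/or DBP > 80 mmHg" (Section 5). The number of readings behind that judgement, and where they are taken, are not stated.

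Section 7 expects, at p < 0.05, that a "greater proportion of patients in the after study period will be in proper control of their hypertension", with control meaning below 130/80 mmHg. Section 11 says that mean readings will be "compared for the pre- and post-periods, as will the number of patients in and out of blood pressure control". It then names the tests: "Pre- and post-study data will be analyzed using a comparison of means (2-tail t-test) and chi-square for comparing low compliant patients". The sentence goes on to name high-compliance patients as the comparison group. The t-test is not said to be paired.

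The home monitor is supplied by the study and "will be given to the patient to monitor blood pressure at home daily" (Section 6). No run-in is described. In the weekly calls "the study pharmacists will counsel the patients on their blood pressure readings for that week". One secondary objective is "To determine if blood pressure readings improve with pharmacist interventions" (Section 3).

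Section 8 was not in the text available for review, so a definition given there could not be checked.

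**The concern.** The before/after comparison depends on what counts as before, and the text leaves that open. One candidate is the reading that made the patient eligible. Nobody can be controlled at that reading: eligibility requires more than 130 or more than 80, and control requires less than both. The proportion controlled then starts at zero and can only rise. Some patients who qualified on a chance high reading will be below the threshold next time, whatever the pharmacist does. Mean blood pressure drifts down for the same reason.

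The primary objective is to produce data for designing a larger study, and a secondary objective ties improvement to the pharmacist. A rise produced by retesting could be reported as a pharmacist effect and carried forward as the planning effect size, which would leave the larger study too small.

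A lesser gap is that no paired test is named for control status. Read narrowly, the chi-square covers only the compliance comparison, so the Section 7 hypothesis has no test. Read broadly, it treats 20 pairs as 40 independent people.

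**Working it through.** **Inputs from the documents.** n = 20; eligibility SBP > 130 and/or DBP > 80; control < 130/80; p < 0.05. The documents give no SD, correlation, control rate, effect size or power, so the 20 cannot be reproduced and the inputs in steps 2 to 5 are assumptions.

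**1. How many newly controlled patients give p < 0.05 from 0/20?** With b patients gaining control and none losing it:
- Exact McNemar, two-sided: p = 2 × 0.5^b. For b = 5, p = 0.0625; for b = 6, p = 0.031. Six are needed.
- Asymptotic McNemar: chi-square = (b − 0)²/(b + 0) = b. For b = 4, p = 0.046. Four are needed.
- Unpaired Pearson, 0/20 v 4/20: 40 × (0 × 16 − 20 × 4)² / (20 × 20 × 4 × 36) = 4.44, p = 0.035. Four are needed.

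At four patients, exact McNemar gives 0.125. The asymptotic paired and unpaired tests differ only as 0.046 v 0.035, so pairing alone changes p little.

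**2. How many eligible patients are controlled on retest with no true change?** Assumed: bivariate normal readings; pool mean 130/78 to 142/84; single-reading SD 16/10; within-person SD 8/5 to 12/7; SBP/DBP correlation 0 to 0.9; eligibility on one reading; retest on one reading or a mean of 7. Over 90 settings, 3% to 32% are controlled, median 13%.

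**3. Chance of p < 0.05 from a baseline of 0/20.** With retest rate q, the number controlled is binomial(20, q):

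| q | 4 or more (Pearson, asymptotic McNemar) | 6 or more (exact McNemar) |
|---|---|---|
| 3% (lowest) | 0.2% | < 0.01% |
| 10% | 13% | 1% |
| 13% (median; 12.8% unrounded) | 25% | 3.5% |
| 20% | 59% | 20% |
| 25% | 77% | 38% |
| 32% (highest) | 92% | 66% |

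If eligibility rests on a mean of 3 readings, the median q falls to 10.5%, and the median rejection rates to about 15% and 1.4%.

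**4. Before and after both taken from readings not used for eligibility, no true change.** With sets of 7 readings, rejection is at most 0.3% (exact McNemar), 0.6% (Pearson) and 3.7% (asymptotic McNemar) over 45 settings. With sets of 3, it is at most 0.8% (exact) and 4.9% (asymptotic). None exceeds 5%.

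**5. Mean SBP, before = qualifying reading.** This uses a different set of assumptions: between-patient SD 12/8, within-patient SD 6/4 to 10/6, correlation 0.6, pool mean 125/75 to 140/83. A paired t-test finds a significant fall in about 5% to 52% of trials with no true change. At the upper end, the mean change is −4.6 mmHg with SD 9.8, so the noncentrality is −4.6/9.8 × √20 = −2.1.

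**The case against.** The strongest reply is that the qualifying reading is not the most natural meaning of before. Section 11 speaks of mean readings over periods and of automatic capture in Epic. Sections 6 and 13 describe that capture as the home device feeding through the phone. Six weekly calls in an eight-week study leave 8 − 6 = 2 weeks that could hold early and late readings. A mean of earlier clinic values is also possible, and that would not force baseline control to zero. This stands as far as it goes: the home-reading interpretation is open, and under it step 4 shows no inflation. But the text does not choose it.

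The size of the risk also depends on the test and the assumptions. With exact McNemar, the median setting is below 5%, and just over half of the 90 settings (about 56%) are at or below 5%. The largest figures combine the uncorrected tests with high retest rates. Blood pressure change is a secondary objective in a pilot, and its p < 0.05 appears under expected results.

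A reader might infer that the plan uses the qualifying reading as its baseline, or that a false-positive result is likely. The documents support neither: they do not choose the baseline, and the retest rate is not given. Nor do they support the view that an unpaired chi-square would by itself create false positives. With separate sets of 7 readings it is conservative, rejecting at most 0.6% of the time.

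**Conclusion.** The point holds in conditional form. The available text does not define the before period, and one meaning that it allows lets both the control comparison and the mean comparison reach p < 0.05 with no pharmacist effect. On that meaning, with one qualifying reading, the median chance for control is about 25% with uncorrected chi-square or asymptotic McNemar and about 3.5% with exact McNemar, with wide ranges around both. Several qualifying readings make it smaller, and readings separate from eligibility remove it. A change from a clinic qualifying reading to home readings could add to the artefact, but the documents do not give the setting.

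The unnamed paired test, and the t-test not said to be paired, are wording gaps with little effect on p. Confidence is high that the before period is undefined in the text reviewed, and moderate for the size of the false-positive risk, which rests entirely on assumed inputs. It should be fixed before analysis because the pilot's results are meant to plan a larger study.

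**What to change.** In Section 11:

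(a) Define before as the mean of home readings between the initial visit and the first weekly call. Define after as the mean of the same number of readings in the last study week. Use the same device for both, and use neither for eligibility.

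(b) Analyse mean blood pressure with a paired t-test and 95% CI. For control, lead with the paired difference in proportions and its 95% CI (a Tango score interval is one option), with a McNemar-type test in support. For example, 6 gained and 0 lost of 20 gives +30 points, CI 9 to 52, exact p = 0.031.

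(c) If only the qualifying reading is available as before, report the after-period proportion with an exact CI (6/20 gives 12% to 54%). Do not present a before/after p-value, for control or mean blood pressure, as evidence of a pharmacist effect, and do not use that change as the planning effect size.

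The cost is a few lines of wording and no new data. There are downsides:
- The timing of the first call is not stated, so pre-call readings may be few. They also follow the teaching at the initial visit, so an immediate effect would be partly missed.
- Exact McNemar is conservative at n = 20. For an assumed rise from 10% to 40% (3% losing control), its power is 50% v 69% for the asymptotic version; for 20% to 50% (5% losing control), 45% v 60%.
- The score interval and the exact test can disagree near 0.05 (7 gained, 1 lost: CI 3 to 54, p = 0.070), which is why the interval should lead.
- Without a control group, other changes over time remain mixed with any pharmacist effect.

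### Device use is split into low and high groups for a chi-square in about 20 patients, although daily Epic readings give a graded count per patient (minor, exploratory)

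*Combined protocol and SAP*

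**What the plan says.** Section 11 describes the compliance analysis in one clause: "chi-square for comparing low compliant patients (for using the devices) with high compliant patients". The same sentence also names a two-tailed t-test. It does not say whether that test is only for the before/after comparison or also for low versus high compliers, and it does not name the outcome crossed with compliance.

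Three other statements bear on the point:

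- **Sample size.** Section 5: "We are aiming to enroll 20 patient participants for this pilot study".
- **Data on device use.** Section 6 says phones "will be used to monitor blood pressure once a day, and results will be sent automatically", and section 11 repeats that "BP readings will be captured automatically in Epic".
- **Possible outcome.** Just before the compliance clause, section 11 says mean BP will be compared between periods, "as will the number of patients in and out of blood pressure control". Section 7 expects that a "greater proportion of patients in the after study period will be in proper control of their hypertension".

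No graded analysis of device use appears in the available text. Section 8 is not part of that text, so a cut-point, counting window or outcome may be given there. Their absence is therefore noted, not counted as an error.

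**The concern.** Days with a reading is a count with a wide range. Reducing it to low or high treats a patient just above the cut like one who measured every day, and a patient just below it like one who hardly measured at all. With about 20 patients there is little information to spare.

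A second loss would follow if the outcome were BP control. Patients must "have uncontrolled hypertension (SBP > 130 mmHg and/or DBP > 80 mmHg") to enter, so control at the end reduces each patient's BP change to yes or no.

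The stakes are modest. Neither the objectives in section 3 nor the hypotheses in section 7 concern compliance against BP. But the primary objective is preliminary data for a larger study, and an estimated association with its interval serves that better than a p-value from a 2x2 table.

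**Working it through.** The documents give no power, effect size or SD for this comparison, so there is no planned figure to reproduce.

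**Inputs from the documents.** n = 20 (section 5). One reading a day (section 6). Six weeks of weekly follow-up ("Follow-up with patients once per week for six (6) weeks") within eight weeks in total. The count can therefore reach 6 x 7 = 42 days, or 8 x 7 = 56 if the device is used throughout.

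**Assumptions.** Two-sided 5% level; correlation 0.3, 0.5 or 0.7 between adherence and BP change; 35% or 50% of patients controlled at the end, taken as those with the larger BP falls (a simplification, since control also depends on the starting value).

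**Step 1: smooth relation.** Adherence x and BP change y are bivariate normal, y = rho·x + sqrt(1 - rho²)·e. Low means the ten lowest values of x. The chi-square is uncorrected. Power by simulation, n = 20:

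| Analysis | rho 0.3 | rho 0.5 | rho 0.7 |
|---|---|---|---|
| Spearman, both graded | 22% | 57% | 92% |
| t-test of BP change, median split | 17% | 42% | 78% |
| Chi-square on control, median split | 10-12% | 25-28% | 51-56% |

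Splitting adherence alone costs 22 - 17 = 5, 57 - 42 = 15 and 92 - 78 = 14 percentage points. The further drop to the third row comes from also reducing BP change to control status, and applies only if control is the outcome.

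**Step 2: other shapes.** Effects are 0.8, 1.2 and 1.5 SD between low and high adherence, n = 20.

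| Shape | Spearman | Split t-test | Chi-square on control |
|---|---|---|---|
| Step at the centre of adherence | 27/51/68% | 28/52/68% | 17-19/33-37/46-52% |
| Two clusters, 10 and 10 | 30/55/74% | 39/72/89% | 23-26/46-52/64-71% |
| Two clusters, 5 low and 15 high, 50% controlled | 18/32/44% | – | 22/40/56% |
| Same 5 and 15, 35% controlled | 18/33/44% | – | 12/21/27% |

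In the last two rows the clusters were set at 8-19 and 36-42 days. A central step gives Spearman no gain over the split t-test. With two clusters of ten the split t-test wins. With 5 and 15 and half controlled, even the chi-square beats Spearman; at 35% controlled that order reverses.

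**Step 3: precision of the alternative.** For an observed Spearman correlation r = 0.5 at n = 20, SE(z) = sqrt((1 + r²/2)/(n - 3)) = sqrt(1.125/17) = 0.257. Then atanh(0.5) ± 1.96 x 0.257 = 0.549 ± 0.504, and back-transforming gives 0.05 to 0.78.

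**Step 4: the window matters.** A patient who measures daily for six weeks and then stops has 42 days in either window. One who measures 6 days in 7 throughout has 6 x 6 = 36 days over six weeks but 8 x 6 = 48 over eight. Their order reverses, so one window must be named.

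**The case against.** The strongest objection is that section 11 never says BP control is crossed with compliance. Section 6 uses pre- and post- for the surveys, so the chi-square could equally concern categorical survey or demographic items; a correlation with BP change would then answer a different question. The t-test in the same sentence may also be meant for low versus high compliers, which would leave BP change continuous. Both readings are open. A reader might infer that the planned analysis has half the power of Spearman or less; that holds only for control as the outcome and a smooth relation. What remains on the t-test reading is the smaller loss from splitting adherence.

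A reader might also infer that Spearman is better whatever the data look like. The clustered cases in the working contradict this. Unequal clusters are plausible, because section 12 has pharmacists call patients who have gone 48 hours without a reading, which may push most users towards high adherence. Such calls could also create ties at the ceiling or compress adherence until no method shows much.

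Finally, the comparison is exploratory, the interval would be wide, and nothing in section 11 forbids reporting the count as well. That is fair, and it limits the weight of the point. It does not make the split a better default when a graded count is available without extra work.

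**Conclusion.** The concern holds as a minor, exploratory point. A graded count exists and the stated analysis does not use it. Under a smooth relation with n = 20, splitting adherence alone lowers power from about 22/57/92% to 17/42/78% at assumed correlations of 0.3/0.5/0.7. The larger fall, to about 10-12/25-28/51-56%, is conditional on BP control being the outcome, which is inferred and not stated.

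The effect sizes, control rates and shapes are all assumptions. The documents do not support a claim that the chi-square is always the weaker choice. Nor do they support a charge that the cut is left open to choice after the data are seen, since section 8 was not available. No objective or hypothesis of the trial is put at risk.

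**What to change.** Where the compliance comparison concerns BP, replace the low/high chi-square clause in section 11 with wording such as:

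> Adherence is the number of days with at least one home reading in Epic during the six weeks (42 days) of weekly follow-up. Its association with each patient's change in mean SBP, and supportively DBP, from the planned pre- and post-period means is estimated by Spearman correlation (mid-ranks for ties) with a 95% CI. This analysis is exploratory; adherence is not randomised.

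If the team prefers all eight weeks, state that instead, but use one window. Any low/high table should be descriptive, with its cut fixed before BP results are viewed. If the chi-square is meant for survey or demographic items, say so; this replacement then does not apply to it.

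The cost is a few sentences and no new data. The downsides are:

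- a wide interval at n = 20;
- a loss against a split analysis if adherence is clustered;
- possible ties or compression from the reminder calls;
- noisier post-period means in patients with few readings;
- dependence on a defined pre-period mean, which the planned before/after comparison needs anyway.

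### The low- versus high-compliance comparison takes no account of starting BP, so a difference in where patients began can appear as an effect of device use

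*Combined protocol and SAP*

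**What the plan says.** Section 11 says that mean BP and the number of patients in and out of control will be compared between the pre- and post-periods. It then names two methods: a "comparison of means (2-tail t-test") and a "chi-square for comparing low compliant patients (for using the devices) with high compliant patients". For the second it gives no outcome, no cut-point between low and high, no measure of device use and no covariate.

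The surrounding facts are these:
- Section 4: "This is a pragmatic before and after trial with the patient serving as their own control".
- Section 5: "We are aiming to enroll 20 patient participants for this pilot study". Patients must "have uncontrolled hypertension (SBP > 130 mmHg and/or DBP > 80 mmHg"), and this criterion sets no upper limit.
- Section 7: success is being "in proper control of their hypertension ($< 130/80$ mmHg"). The significance level is given only for the before/after hypothesis ("A statistically significant ($p < 0.05$) greater proportion of patients in the after study period").
- Section 12: pharmacists telephone patients who have gone 48 hours without a reading, so staff contact also influences device use.

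Nothing in the text available for review adjusts for, stratifies by or tabulates baseline BP by compliance group. Section 8 was not in that text and could not be checked.

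**The concern.** Using each patient as their own control removes stable differences between patients from the before/after comparison. It does nothing for a comparison between two sets of patients. Those sets are formed by the patients' own behaviour after entry, and a chi-square on a two-by-two table cannot take account of where each patient began.

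Starting BP matters because control is a fixed threshold. Everyone enters above 130 systolic and/or 80 diastolic, but a patient starting at 132 needs a much smaller fall to reach control than one starting at 155. If the high-use group starts lower, it will show more control for that reason alone. If it starts higher, a real benefit of device use could be hidden.

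The stated primary objective is to produce preliminary data for a larger study. A table showing better control among heavier users could be carried into that design as evidence about adherence when it reflects only starting BP.

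**Working it through.** The plan states no power, SD or expected effect, so there is no figure to reproduce. The size of the bias has to be shown on assumed inputs.

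**From the documents:** 20 patients; SBP control threshold 130 mmHg; two-sided testing (stated for the t-test); 0.05 level (stated for the before/after hypothesis).

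**Assumed:** a 10 v 10 split; baseline SBP SD 10 mmHg; mean baseline 138 in the low-use group and 133 in the high-use group, a systematic 5 mmHg gap; control judged on SBP only; no effect of device use. Final SBP = 132 + 0.7 × (baseline − 138) + error, with error SD 7.

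**Step 1: spurious difference in control.**
- SD of final SBP = √(0.7² × 10² + 7²) = √98 = 9.90.
- Mean final SBP: low use 132; high use 132 − 0.7 × 5 = 128.5.
- Share below 130: low use Φ((130 − 132)/9.90) = 0.420; high use Φ((130 − 128.5)/9.90) = 0.560.
- Difference = 0.140, or 14 percentage points, with no effect of device use.

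**Step 2: false-positive rate of the planned test.** Enumerating every 10 v 10 table with these two probabilities, at the 0.05 level:

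| Baseline gap | Difference in control | Chi-square, uncorrected | Chi-square, continuity-corrected |
|---|---|---|---|
| 0 mmHg | 0 points | 4% | 1% |
| 5 mmHg | 14 points | 8% | 3% |
| 10 mmHg | 27 points | 21% | 10% |

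**Step 3: a different baseline shape.** Let all baseline SBPs lie above 130 (130 plus a gamma variable with shape 2), with group means of 138 and 143, the same mean fall of 8 to 12 mmHg in both groups, and SD of change 8 to 12. The spurious difference is then 12 to 17 points. Rejection is 7–10% uncorrected and 3–4% corrected, so the result does not depend on the normal baseline of Step 1.

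**Step 4: if the outcome is change in BP.** Under the Step 1 model, change = constant − 0.3 × baseline + error, because high starters fall further through regression to the mean.
- Difference in mean change at a 5 mmHg gap = 0.3 × 5 = 1.5 mmHg.
- SD of change = √(0.3² × 10² + 7²) = √58 = 7.62.
- A t-test on change has noncentrality 1.5 / (7.62 × √(2/10)) = 0.44 on 18 df, and rejects in about 7%.

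The bias is smaller than for control status and runs the other way: the group that starts higher appears to improve more.

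**Step 5: with baseline as covariate.** Simulating the same 5 mmHg gap, the linear model for final SBP rejects in about 5%, the nominal rate, and its estimated effect of device use averages about zero.

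**The case against.** The strongest objection is that the plan does not name the outcome. The chi-square may concern change in control status, or something other than BP, so it is not established that baseline is ignored in every reading. This stands, and the point is conditional for that reason. It does not remove the point: for control status the bias is direct, and for BP change it persists through regression to the mean.

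It is also fair to say that the comparison appears in neither the objectives nor the hypotheses, that this is a 20-patient pilot, and that the 5 mmHg gap is assumed. All three limit the importance of the point.

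A reader might infer three stronger things that the documents do not support.

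- **That the planned test will often be falsely significant.** An unadjusted t-test on final mean SBP would reject in about 12% at a 5 mmHg gap, but that is not the planned test. The chi-square rejects in 8% or 3%, depending on the correction.
- **That chance imbalance between small groups inflates the error rate.** It does not. A test's nominal level already allows for chance differences, and the no-gap row of the table is below 5%. The excess needs a systematic link between starting BP and device use, for which the documents give no figure.
- **That the recheck rule in Section 6 makes high-BP patients look more compliant** ("If any patient has an SBP reading > 160 mmHg or DBP > 100 mmHg, they will be instructed to wait five minutes"). This would follow only if use were counted in readings. The plan does not say so, and its daily monitoring schedule and 48-hour call trigger point towards counting days.

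**Conclusion.** The concern holds in a limited form. As written, the compliance comparison is unadjusted between self-selected groups. If its outcome is BP control, a systematic difference in starting BP produces a difference in control with no effect of device use: about 14 points for a 5 mmHg gap, 12 to 17 under an alternative baseline shape. Under either shape the chi-square's false-positive rate at that gap is at most about 10% uncorrected and stays below 5% with the correction. The harm is thus mainly a misleading point estimate.

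These sizes rest on the assumed split, SD, gap and regression slope. The direction of the bias depends on which group starts lower, which cannot be known in advance. The point is minor: it concerns an unlisted comparison in a pilot, and is worth making because the remedy uses BP data already planned for collection.

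**What to change.** In Section 11, replace the chi-square with a linear model of each patient's final-period SBP on device use, with baseline SBP as the only covariate. Define device use as the number of days with at least one reading before the final BP window opens, so that use precedes outcome and repeat readings on one day do not count twice. State which readings form the baseline and the final window, since the plan does not define either period. Show baseline BP by level of device use. Report the estimate with a 95% CI as an exploratory, non-causal association.

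The cost is a few sentences, one degree of freedom and a more cautious claim. No new data are needed. Two limits should be stated with the result:
- Adjustment for baseline SBP does not remove other self-selection, or the effect of the 48-hour calls on device use.
- Precision will be low. Under the assumed error SD of 7, a 10 v 10 contrast has a standard error of at least 7 × √(2/10) = 3.1 mmHg, so a 95% CI of at least ±2.11 × 3.13 = ±6.6 mmHg (t on 17 df).
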